## 4 Statistical Analyses

### 4.1 General Considerations

The one-sided test used for the primary endpoint is based on an alpha level of 2.5%. All other statistical tests conducted will be two-sided on the 5% significance level.

Two factors are defined as follows:

- Age group: Age at randomisation (<6 versus  $\geq 6$  years)
- GH peak group: Growth hormone peak level (< 7 versus  $\geq 7$  ng/ml)

All efficacy endpoints will be analysed using FAS and all safety endpoints will be analysed using SAS.

The primary endpoint will additionally be analysed using PP as a support to the results achieved using FAS under the hypothetical strategy.

### 4.2 Primary Endpoint Analysis

The primary analysis of the primary endpoint Height velocity (cm/year) at week 52, addressing the primary estimand is based on the FAS but data assessed after discontinuation of randomised treatment will be disregarded in the analysis.

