### **6.4 Treatment compliance**

#### **Drug treatment compliance**

Throughout the trial, the investigator will remind the subjects to follow the trial procedures and requirements to encourage subject compliance.

When subjects are dosed at the site, they will receive trial product directly from the investigator or designee, under medical supervision. The date and time of each dose administered at the site will be recorded in the source documents.

When subjects self-administer trial product(s) at home, compliance with trial product administration will be assessed and the assessment documented in source documents at each visit where information is available. Any missed dose should be discussed with the subject and followed up to ensure subject is compliant to trial product and trial procedures. If any suspicion of non-compliance arises i.e, 30% of the missed doses of somapacitan or Norditropin® between two visits the site must enter into a dialogue with the patient, re-emphasizing the importance of compliance and uncover barriers to compliance. This dialogue must be documented. Compliance will be assessed by cross checking the following sources and comparing these to the expected use:

- Drug accountability information; counting returned trial product, visual inspection of pens
- Review of dosing diaries
- Questioning of subjects

Treatment start dates, stop dates and all doses will be recorded in the electronic case report form (eCRF).

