## **7.1 Discontinuation of trial treatment**

A subject who does not fulfil the eligibility criteria (inclusion/exclusion criteria) must not be randomised. Randomisation in violation of any of the eligibility criteria is a Good Clinical Practice (GCP) non-compliance and must be reported to the sponsor without delay. This will be handled as an important protocol deviation, and the independent ethics committee (IEC)/ institutional review board (IRB) and regulatory authorities must be notified according to local requirements. If there are no safety concerns, trial treatment may be continued or resumed at the discretion of the investigator after agreement with the sponsor's global medical expert.

The trial product must be discontinued, if any of the following applies for the subject:

1. Safety concern related to trial product or unacceptable intolerance
2. Simultaneous use of an approved or non-approved investigational medicinal product in another clinical trial
3. Tumour development

See the flowchart [1.2](#) for data to be collected at the time of treatment discontinuation (early discontinuation visit) and follow-up and for any further evaluations that need to be completed.

The purpose of the follow-up visit is to collect information about adverse events. For convenience of the subject the follow up visit can be performed as a telephone contact. The follow up visit should be performed as a site visit for subjects with an ongoing injection site reaction at visit 8.

The primary reason for discontinuation of trial product must be specified in the end-of-treatment-form in the CRF, and final drug accountability must be performed. A treatment discontinuation session must be made in the IWRS.

If a subject discontinues treatment prior to visit 7, Visit 7A should be performed at least 7 days after the last dose of trial product and prior to starting treatment with marketed product. The follow up visit should be performed 30 days after the last dose of trial product.

Although the treatment has been discontinued, the subject will continue to follow the planned visit schedule until visit 7 (52 weeks).

If the subject or family refuse to attend planned visit schedule, then efforts should be made for the subject to attend visit 7 as it is the primary endpoint visit.

After visit 7A the following assessments are not applicable for subjects who discontinue trial product:

- Trial drug administration
- Drug accountability
- PK and Antibody sampling

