### 9.3      Populations for analyses

The following populations are defined:

Population	Description
Full analysis set	Full analysis set (FAS): All subjects randomised. Exclusion of data from analyses should be used restrictively, and normally no data should be excluded from the FAS. Subjects will be analysed according to the randomised treatment
Safety analysis set	Safety analysis set (SAS): All subjects randomly assigned to trial treatment and who take at least 1 dose of trial product. Subjects are analysed according to the treatment they actually received.
Per protocol analysis set	PP: Subjects from FAS who have not violated any inclusion/exclusion criteria and have used the randomised treatment for at least 47 weeks (for subjects receiving somapacitan) or 329 days (for subjects receiving Norditropin) corresponding to 90% of the planned exposure. Subjects are analysed according to the treatment they actually received.

The subjects or observations to be excluded, and the reasons for their exclusion must be documented before unblinding. The subjects and observations excluded from analysis sets, and the reason for this, will be described in the CTR. Two observation periods are defined:

- on-treatment: from first administration and up until last trial contact, visit 7 or 14 days after last administration, whichever comes first
  - in-trial: from first administration and up until last trial contact or visit 8, whichever comes first
- Analysis based on the 'in-trial' observation period is to be viewed as supplemental analysis to the analysis based on the 'on-treatment' analysis.

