### 9.4.2 Primary endpoint(s)

The primary endpoint:

- Height velocity (cm/year) at week 52

will be derived from height measurements taken at baseline and the week 52 visit (landmark visit) in the following way:

$HV = (\text{height at 52 weeks visit} - \text{height at baseline}) / (\text{time from baseline to 52 weeks visit in years})$ .

Annualized HV at the intermediate visits: Week 13, 26 and 39, will be derived analogously to the week 52 HV:  $HV = (\text{height at } j \text{ weeks visit} - \text{height at baseline}) / (\text{time from baseline to } j \text{ weeks visit in years})$ ,  $j=13, 26, 39$ .

The primary analysis of the primary endpoint addressing the primary estimand described in section 3.1 is based on the FAS but data assessed after discontinuation of randomised treatment will be disregarded in the analysis.

In order to estimate the primary estimand, a mixed model for repeated measurements (MMRM) with an unstructured covariance matrix is conducted on HV data (annualized HV at planned visits at week 13, week 26, week 39 and week 52) up to discontinuation of randomised treatment for each treatment arm using all randomised subjects and assuming missing at random (MAR) for both treatment arms. The MMRM will include sex, age group, GH peak group and sex by age group interaction term as factors and baseline height as a covariate, all nested within week as a factor. From this analysis an estimate of the treatment difference at week 52 with corresponding 95% CI will be presented.

Non-inferiority of somapacitan will be considered confirmed if the lower boundary of the two-sided 95% confidence interval is above -2 cm/year.

A tipping point analysis will be conducted as a sensitivity analysis for the analysis of the primary endpoint for the primary estimand. For this analysis, the missing data are expected to be mainly due to subjects that are withdrawn from the trial or discontinue randomised treatment. The sensitivity analyses described below will be used to investigate whether the results from the primary analysis are robust against departures from the assumption of MAR.

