**For subjects randomised to somapacitan:**

**Table 15      Timing of visits and blood sampling**

Visit	Timing of visit
3	1 to 4 days after dosing
4	On a planned dosing day
5	1 to 4 days after dosing
6	On a planned dosing day
7	4 to 6 days after dosing
8	No blood sampling

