### 3 Analysis Sets

The following populations are defined:

Population	Description
Full analysis set (FAS)	All subjects randomised. Exclusion of data from analyses should be used restrictively, and normally no data should be excluded from the FAS. Subjects will be analysed according to the randomised treatment
Safety analysis set (SAS)	All subjects randomly assigned to trial treatment and who take at least 1 dose of trial product. Subjects are analysed according to the treatment they actually received.
Per protocol analysis set (PP)	Subjects from FAS who have not violated any inclusion/exclusion criteria and have used the randomised treatment for at least 47 weeks (for subjects receiving somapacitan) or 329 days (for subjects receiving Norditropin) corresponding to 90% of the planned exposure. Subjects are analysed according to the treatment they actually received.

The subjects or observations to be excluded, and the reasons for their exclusion must be documented before unblinding. The subjects and observations excluded from analysis sets, and the reason for this, will be described in the CTR. Two observation periods are defined:

- on-treatment: from first administration and up until last trial contact, visit 7 or 14 days after last administration, whichever comes first
- in-trial: from first administration and up until last trial contact or visit 8, whichever comes first

Analysis based on the 'in-trial' observation period is to be viewed as supplemental analysis to the analysis based on the 'on-treatment' analysis.

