## 4.2.2 Main Analytical Approach

In order to estimate the primary estimand, a mixed model for repeated measurements (MMRM) with an unstructured covariance matrix is conducted on HV data (annualized HV at planned visits at week 13, week 26, week 39 and week 52) up to discontinuation of randomised treatment for each treatment arm using all randomised subjects and assuming missing at random (MAR) for both treatment arms. The MMRM will include sex, age group, GH peak group and sex by age group interaction term as factors and baseline height as a covariate, all nested within week as a factor. From this analysis an estimate of the treatment difference at week 52 with corresponding 95% CI will be presented.

Non-inferiority of somapacitan will be considered confirmed if the lower boundary of the two-sided 95% confidence interval is above -2 cm/year.

The primary endpoint will be analysed based on the ‘on-treatment’ observation period.

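### Do the two cut-offs for the primary height data, discontinuation and the 14-day on-treatment period, leave the primary analysis undefined?

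*SAP*

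**What the plan says.** Protocol 9.4.2 states that the primary analysis "is based on the FAS but data assessed after discontinuation of randomised treatment will be disregarded in the analysis". SAP 4.2 repeats that "data assessed after discontinuation of randomised treatment will be disregarded in the analysis", and the model paragraph of SAP 4.2.2 uses height velocity (HV) up to discontinuation. Neither document says which date counts as discontinuation, although Protocol 6.4 has the dates collected: "Treatment start dates, stop dates and all doses will be recorded in the electronic case report form".

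The closing sentence of SAP 4.2.2 begins "The primary endpoint will be analysed based on the" and then names the on-treatment observation period. Protocol 9.3, and SAP 3 in the same terms, define it as "on-treatment: from first administration and up until last trial contact, visit 7 or 14 days after last administration, whichever comes first". Both make this the main period and the in-trial period supplemental.

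For a child who stops early, Protocol 7.1 says "Visit 7A should be performed at least 7 days after the last dose of trial product and prior to starting treatment with marketed product". For somapacitan, Table 15 in Protocol Appendix 2 puts visit 7 at "4 to 6 days after dosing".

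The estimand (Protocol 3.1, SAP 1.1.5) concerns the treatment difference had ancillary therapy not been available. Protocol 9.2 and SAP 5 give the link to discontinuation: children who stop are expected to move to ancillary treatment unless there is a medical reason not to, so data after discontinuation are left out.

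**The concern.** Applied separately and literally, the two rules keep different heights.

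- **Early stoppers.** If discontinuation is dated at the last dose, a planned visit 1 to 14 days later is after discontinuation but still on-treatment. From day 7, when visit 7A becomes possible, such a height could even follow the start of marketed growth hormone, which is the event the estimand excludes.
- **Late visit 7.** A child who never discontinued, but whose visit 7 came more than 14 days after the last dose, falls outside the on-treatment period. SAP 1 and SAP 4.2.3.2 expect delayed visits and plan to use those heights.
- **Estimand.** The estimand names ancillary therapy, whereas the data are cut at discontinuation. A child who stops and never starts ancillary therapy is cut as well.

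At stake is which heights enter the single confirmatory test, in an open-label trial whose SAP was written after first patient first visit.

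**Working it through.** **Inputs.** From Protocol 9.2 and SAP 5: 108 children randomised 2:1 (72 and 36), 10% without usable landmark data, margin 2.0 cm/year, SD 2.6 cm/year, one-sided 2.5%, true difference 0. From Protocol 4.2: growth hormone effect against no treatment of 3.3 to 4 cm/year. Assumption: stopping times are even over 364 days.

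**1. The plan's own power.** After 10% loss the arms hold 64.8 and 32.4 children.
- SE = 2.6 × √(1/64.8 + 1/32.4) = 0.559.
- Two-sample t-test power is 95.7%, 94.3%, 92.6% and 90.8% for SD 2.5, 2.6, 2.7 and 2.8. The plan states 95%, 94%, 92% and 90%, so its table is reproduced.

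**2. Children with a disputed height.** Early stoppers: 0.10 × 108 = 10.8 (7.2 somapacitan, 3.6 Norditropin). Dating discontinuation at the last dose gives the widest gap, 14 days.
- Week 52: 10.8 × 14/364 = 0.42 children.
- All four visits: 4 × 0.42 = 1.66 children.
- Days 7 to 14 only, where marketed growth hormone could have started: 10.8 × 7/364 = 0.21 children at week 52.

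These are upper-end figures, because the 10.8 includes children who attend no later visit.

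**3. Expected shift at week 52.** Fourteen days without benefit costs 14/365.25 × 3.3 to 4 = 0.13 to 0.15 cm, close to the 1 mm recording unit in Protocol 8.1.1.1.
- Somapacitan children affected: 7.2 × 14/364 = 0.28 of 72, or 0.4%.
- Shift in the arm mean: 0.004 × 0.15 = 0.0006 cm/year, or 0.03% of the margin.
- Norditropin: 3.6 × 14/364 = 0.14 of 36, also 0.4%. With equal rates the shift cancels in the difference.

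A single height moving in or out also has a chance effect. For a child one SD from the mean it is about 2.6/64.8 = 0.04 cm/year in the somapacitan arm or 2.6/32.4 = 0.08 in the Norditropin arm. It has no systematic direction and is small against an SE of 0.56.

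**4. Tipping-point analysis.** The CI half-width is 1.111. At an observed difference of 0 and f1 = 0.10, the one-arm tipping value is (2 − 1.111)/0.10 = 8.9 cm/year. If the disputed heights are kept, f1 falls to about 0.096 and the value becomes 0.889/0.096 = 9.3. Both are far above the 3.3 to 4 cm/year effect.

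**5. Late visit 7.** With visit 7 planned 4 to 6 days after a somapacitan dose, the 14-day limit is passed only if the visit is more than 14 − 6 = 8 to 14 − 4 = 10 days late and no further dose was given. If weekly dosing continued, the last dose is at most 7 days old, or 10 with the 3-day late allowance in Protocol 6.1, and the height stays in. The documents do not say whether dosing continued. If 2%, 5% or 10% of completers lost their week-52 height (assumed shares), power would be 93.9%, 93.2% or 91.8%. The repeated-measures model would recover part of that from week 39.

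**6. Estimand.** Protocol 6.5.1 does not allow ancillary therapy on trial product, and Protocol 6.7 allows marketed growth hormone once trial product stops. Under compliant conduct, a cut at discontinuation therefore removes every height taken after ancillary therapy. For children who stop and stay untreated, the gap is 0 at the equal rates the plan assumes. With an assumed 10% against 5% discontinuation and half a year off treatment, it is 0.05 × 0.5 × (3.3 to 4) = 0.08 to 0.10 cm/year if all stay untreated, and about 0.02 if a quarter do. The plan's expectation that stoppers switch to a marketed product points to the low end.

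**The case for a change.** The strongest case for a change is that two programmers could build different primary datasets from SAP 4.2 and from the last sentence of SAP 4.2.2. The on-treatment sentence is absent from Protocol 9.4.2, yet SAP 4.8 reports no changes. A fix would cost a few words, and the dates are already collected.

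The missing link stands: nothing states that the 14-day period dates discontinuation. The rest is weaker.

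- The on-treatment sentence is hardly a new rule. Protocol 9.3 already makes that period the main one, and SAP 4.2.2 puts both statements in one section.
- SAP 3 requires excluded observations and reasons to be documented before unblinding, so the choice cannot follow the results.
- SAP 4.2.3.2 interpolates back to week 52 to see what the delay did. That comparison makes sense only if the primary analysis uses the delayed height, with HV divided by actual elapsed time.
- Heights after ancillary therapy taken alongside trial product would need a protocol violation.

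The obvious remedies also have drawbacks. Dating discontinuation at last dose plus one dosing interval would give the arms different windows in an open-label trial. It could also cut a height taken 8 to 10 days after a somapacitan dose, although the 3-day allowance had not yet run out. Adding discontinuation to the estimand in the SAP alone would make the SAP differ from the protocol.

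**Conclusion.** No change is needed. The SAP leaves out a linking sentence, but the sensible reading is available: the 14-day on-treatment period puts a date on discontinuation, identically in both arms, and a late visit 7 height is kept for a child who did not discontinue. The cut at discontinuation serves the ancillary-therapy estimand under compliant conduct.

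The choice of reading affects about 0.4 children at week 52 and shifts an arm mean by less than 0.001 cm/year in expectation. Sample size, margin and the 94% power stay as stated. This rests on the plan's 10% loss at similar rates in both arms and on even stopping times. The number of delayed visits without continued dosing is unknown, but even a literal exclusion of 10% of completers would leave power near 92%. A marked imbalance in discontinuation would raise a missing-data question, which the planned tipping-point analysis addresses under either reading.

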#### 4.2.1 Definition of Endpoint

The primary endpoint: Height velocity (cm/year) (HV) at week 52

- HV will be derived from height measurements taken at baseline and the week 52 visit (landmark visit) in the following way:

$HV = (\text{height at 52 weeks visit} - \text{height at baseline}) / (\text{time from baseline to 52 weeks visit in years})$ .

Annualized HV at the intermediate visits: Week 13, 26 and 39, will be derived analogously to the week 52 HV:  $HV = (\text{height at } j \text{ weeks visit} - \text{height at baseline}) / (\text{time from baseline to } j \text{ weeks visit in years})$ ,  $j=13, 26, 39$ .

## 4.2.2 Main Analytical Approach

In order to estimate the primary estimand, a mixed model for repeated measurements (MMRM) with an unstructured covariance matrix is conducted on HV data (annualized HV at planned visits at week 13, week 26, week 39 and week 52) up to discontinuation of randomised treatment for each treatment arm using all randomised subjects and assuming missing at random (MAR) for both treatment arms. The MMRM will include sex, age group, GH peak group and sex by age group interaction term as factors and baseline height as a covariate, all nested within week as a factor. From this analysis an estimate of the treatment difference at week 52 with corresponding 95% CI will be presented.

Non-inferiority of somapacitan will be considered confirmed if the lower boundary of the two-sided 95% confidence interval is above -2 cm/year.

The primary endpoint will be analysed based on the ‘on-treatment’ observation period.

## 4.2.3 Sensitivity Analysis

### 4.2.3.1 Tipping point analysis

A tipping point analysis will be conducted as a sensitivity analysis for the analysis of the primary endpoint for the primary estimand. For this analysis, the missing data are expected to be mainly due to subjects that are withdrawn from the trial or discontinue randomised treatment. The sensitivity analyses described below will be used to investigate whether the results from the primary analysis are robust against departures from the assumption of MAR.

Let  $\delta$  be defined as the difference between the mean of the observed data and the mean of the unobserved data  $\mu_{\text{obs}} - \mu_{\text{unobs}}$ , adjusted for other observed data. Under an MAR analysis,  $\delta$  is assumed to be 0. Positive values of  $\delta$  indicate that subjects with missing endpoint values have smaller HV than subjects with observed endpoint values. If subjects primarily withdraw or discontinue randomised treatment/start ancillary therapy due to a perceived lack of efficacy, then this could be the most likely direction of departure from MAR. Let  $f_1$  and  $f_0$  be the fractions of subjects with unobserved endpoint data in the somapacitan and Norditropin® arms, respectively. The sensitivity analysis is done by subtracting a quantity  $\Delta$  from the treatment effect estimate under the MAR assumption, where  $\Delta = f_1\delta$  if data depart from MAR in the somapacitan arm only,  $\Delta = -f_0\delta$  if data depart from MAR in the Norditropin® arm only, and  $\Delta = (f_1 - f_0)\delta$  if data depart from MAR in the

same way in both arms. The calculations for the 3 scenarios will use a range of  $\delta$  values increasing from 0 until the resulting 95% CI no longer is completely above -2cm/year for the most conservative evaluation (data depart from MAR in the somapacitan arm only) and the approximation that the standard error of the treatment difference is unaffected by the sensitivity analysis. All subjects from the FAS can be viewed as included in this analysis as subjects with missing endpoint data will be contributing to one of the fraction values f1 and f0.

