## 5 Sample size determination

Approximately 108 subjects will be randomly assigned to trial product.

The sample size calculation is based on the primary estimand. It is expected based on phase 2 trial data (NN8640-4172) that the proportion of subjects with no landmark visit data or who discontinued randomised treatment before landmark visit is 10% with similar withdrawal reasons in the two treatment arms. NN8640-4172 is a global trial, including Japanese subjects, and therefore trial information from 4172 is expected to also be of use when planning for a somapacitan phase 3 trial in China. It is expected that subjects discontinuing their randomised treatment will start on ancillary treatment, if no medical reasons prohibit this. Thus, data assessed after discontinuation of the randomised treatment will not be used for the primary analysis of the primary endpoint based on the primary estimand. Assuming the same proportions of subjects with no landmark visit and subjects discontinuing randomised treatment but have landmark visit data in the two arms leads to the following sample size calculation.

The sample size is determined using a non-inferiority margin of -2.0 cm/year and a one sided two-group t-test with a significance level of 2.5% for a 2:1 randomisation ratio between somapacitan and Norditropin®.

Based on data from NN8640-4172, a standard deviation for HV at week 52 was chosen (SD=2.6 cm/year) for the sample size calculation giving a sample size of 108 subjects. Different SD scenarios with power calculation for the primary analysis are presented in the table below under the assumption of a true difference in annualized HV of 0 cm/year between the two treatment arms.

Table 9 Calculated power with 108 subjects randomised 2:1

SD	2.5 cm/year	2.6 cm/year	2.7 cm/year	2.8 cm/year
	95%	94%	92%	90%

The SD candidates are based on reported SD values from clinical trials: Valtropin phase 3 trial, 52 weeks (SD=2.8, 3.0), OPKO phase 2 trial, 52 weeks (SD=2.1, 2.3, 2.6, 3.5), and NN8640-4172,

phase 2 trial, 52 weeks (SD=2.3, 2.6).

For sensitivity analysis, a one-way tipping point analysis is planned. Based on a penalty of 2 cm/year for subjects in the somapacitan arm who have missing landmark visit data or discontinue randomised treatment before landmark visit, this gives a power of ~92% (adjusted treatment effect  $0.9*0 - 0.1*2 = -0.2$ ).

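### The tipping-point analysis has one effective stress test; better-than-observed growth in missing Norditropin subjects, and opposed departures, are never examined

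*SAP*

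**What the plan says.** The primary analysis is an MMRM under MAR, and the decision rule is a single one: "Non-inferiority of somapacitan will be considered confirmed if the lower boundary of the two-sided 95% confidence interval is above -2 cm/year" (SAP 4.2.2).

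SAP 4.2.3.1, in the same terms as Protocol 9.4.2, defines δ as the mean of observed minus the mean of unobserved values, adjusted for other observed data. Positive δ therefore means that missing subjects grew less. With f1 and f0 the unobserved fractions on somapacitan and Norditropin, the quantity subtracted from the MAR estimate is:

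- f1·δ if only somapacitan departs from MAR;
- −f0·δ "if data depart from MAR in the Norditropin® arm only, and"
- (f1 − f0)·δ if both arms depart in the same way.

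δ starts at 0 and increases until the interval fails for the "most conservative evaluation (data depart from MAR in the somapacitan arm only) and the approximation that the standard error" of the difference is unchanged. The approximation is declared and referenced. The reason given for the sign is conditional: subjects may leave because they perceive a lack of efficacy. SAP 5 and Protocol 9.2 call the analysis one-way and illustrate it with a 2 cm/year penalty on somapacitan.

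**The concern.** A tipping-point analysis should show how far the missing data must depart from MAR, in directions that could hurt the conclusion, before the result is lost. In a non-inferiority comparison, two things lower the estimate: missing somapacitan subjects growing less than observed, and missing Norditropin subjects growing more. The plan examines the first and not the second, and does not combine them.

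The other planned analyses do not fill the gap. SAP 4.2.3.2 deals with late week-52 visits, SAP 4.2.3.3 adds baseline IGF-I SDS as a covariate, and the per-protocol analysis in SAP 4.2.4 reuses the same MAR model. This is therefore the only check on MAR for the sole confirmatory test, and its tipping point may be read as a general statement of robustness when it covers one direction in one arm.

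**Working it through.** **Inputs (SAP 5; same figures in Protocol 9.2)**

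- Margin: "The sample size is determined using a non-inferiority margin of -2.0 cm/year"
- Test: "one sided two-group t-test with a significance level of 2.5% for a 2:1 randomisation ratio between somapacitan and Norditropin"
- Size: "Approximately 108 subjects will be randomly assigned to trial product", hence 72 and 36.
- SD: "a standard deviation for HV at week 52 was chosen (SD=2.6 cm/year"
- Difference: "under the assumption of a true difference in annualized HV of 0 cm/year between the two treatment arms"
- Missing or discontinued: 10%, taken as equal in both arms, leaving 64.8 and 32.4 with usable week-52 data.

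The observed f1, f0, estimate and MMRM standard error are not in the documents. An estimate of −0.5 and missing fractions other than 10% are assumptions.

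**The plan's own figures.** With 65 and 32 evaluable, noncentral-t power at SD 2.6 is 94.1%, against 94% in Table 9. For the 2 cm/year penalty (effect −0.2, distance to margin 1.8) power is 91.9% with all 108 subjects, which matches the stated ~92%. With 10% missing it is about 89%. The calculations below use the 10%-missing basis.

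**Signs of the planned scenarios (δ ≥ 0, fixed SE)**

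- Norditropin-only: subtracting −f0·δ adds f0·δ, so it cannot tip.
- Both arms: f1 − f0 ≤ f1, so the shift never exceeds that of somapacitan-only. It is zero when f1 = f0. Because the range stops when somapacitan-only tips, this scenario cannot fail first.

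**Tipping points, fixed SE.** SE = 2.6 × √(1/64.8 + 1/32.4) = 0.559; t = 1.985; t × SE = 1.111. The result tips when the subtracted quantity equals 2 + estimate − 1.111, which is 0.889 for an estimate of 0 and 0.389 for −0.5.

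**With the uncertainty of the missing fraction included.** The variance becomes SE² + δ1²·f1(1−f1)/72 + δ0²·f0(1−f0)/36. Check for somapacitan-only at δ = 7.66: 0.313 + 58.7 × 0.09/72 = 0.386; SE = 0.622; −0.766 − 1.985 × 0.622 = −2.00. A simulation at δ = 8.86 gave an SE of 0.643, against 0.641 from the formula.

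Results for f1 = f0 = 10% (δ in cm/year, fixed SE / SE with variance term):

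| Departure | In plan? | Estimate 0 | Estimate −0.5 |
|---|---|---|---|
| Somapacitan grows less | yes | 8.89 / 7.66 | 3.89 / 3.61 |
| Norditropin grows less | yes | never (fixed SE) | never (fixed SE) |
| Both grow less, same δ | yes | never (fixed SE) | never (fixed SE) |
| Norditropin grows more | no | 8.89 / 6.93 | 3.89 / 3.39 |
| Opposed, δ per arm | no | 4.45 / 3.95 | 1.95 / 1.84 |

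Unequal loss, estimate 0, fixed SE:

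- f1 = 5%, f0 = 10% (68.4 and 32.4 evaluable, SE 0.555, critical shift 0.900): somapacitan-only tips at 0.900/0.05 = 18.0; Norditropin growing more tips at 0.900/0.10 = 9.0.
- f1 = 10%, f0 = 5% (critical shift 0.909): somapacitan-only tips at 9.1; the planned both-arms scenario tips at 0.909/0.05 = 18.2.

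At equal loss the opposed value is always half the one-arm value, because the shift is (f1 + f0)·δ. For an estimate of 0 and 10% missing, SD 2.8 gives 8.04 against 4.02, and SD 3.5 gives 5.05 against 2.52.

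**At the plan's own 2 cm/year.** Power with somapacitan-only departure is 89.0% (88.5% with the variance term). With 2 cm/year opposed in each arm it is 80.8% (79.0%).

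**The case against.** The scope is declared as one-way and a reason is given for its sign. The algebra is right, and the fixed standard error is openly called an approximation. Non-inferiority rests on the primary interval alone; the tipping analysis has no pass/fail rule. For an estimate of 0, a tipping δ of 8.9 or 7.7 is far above the 3.3 to 4 cm/year that Protocol 4.2 discusses as the effect against no treatment, so either reads as robust. All of this stands, and it makes the point one of scope.

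Several stronger readings are tempting and are not supported.

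- *Two of the three scenarios can never count against non-inferiority.* This is true only of Norditropin-only. The both-arms shift lowers the estimate whenever f1 > f0, which happens about 47% of the time at 72/36 even if both true rates are 10%.
- *Calling somapacitan-only the most conservative evaluation is false.* The sentence concerns the three listed scenarios, and among those it is true.
- *The fixed standard error makes the reported tipping point wrong.* The extra variance arises only if f1 is treated as estimated. Conditional on f1, the standard error does not change.
- *The burden of daily injections implies that Norditropin dropouts would have grown more.* Protocol 2.2.1 reports frequent missed injections, Protocol 2.1 presents weekly dosing as more convenient, and the trial is open-label. These give a reason to leave that is unrelated to growth, which by itself suggests δ near 0. The documents do not establish a large negative δ on Norditropin; they give no ground for leaving that sign out either.

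**Conclusion.** The point holds as a limit of scope. With δ ≥ 0 and a fixed standard error, somapacitan-only alone sets the tipping point and the other two scenarios add no harsher test. The unexamined directions are harsher in identifiable cases: opposed departures whenever Norditropin has missing data (about 4.4 per arm against 8.9 at planning values), and Norditropin alone whenever f0 > f1 (about 9.0 against 18.0 at 5% and 10%). If the estimate were −0.5, opposed departures would tip at 1.95 per arm, just below the plan's own 2 cm/year penalty.

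The fixed standard error is secondary. If f1 is treated as estimated it overstates the one-arm tipping point by about 16% (8.89/7.66) for an estimate of 0 and 8% (3.89/3.61) at −0.5. At a 2 cm/year penalty it costs half a point of power.

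The sizes rest on a two-sample t approximation. An MMRM standard error would be smaller, and all tipping values larger, if covariates and earlier visits explain variance. The missing direction depends on none of these values. A reader should not infer that the primary conclusion is unsafe: nothing here changes the primary analysis or its decision rule. Label: cheap improvement.

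**What to change.** In SAP 4.2.3.1:

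1. Replace the three scenarios with a two-way grid in which δ1 (somapacitan) and δ0 (Norditropin) vary independently and take both signs. The shift subtracted is f1·δ1 − f0·δ0.
2. Report the whole boundary on which the lower 95% limit reaches −2.0 cm/year, with the observed f1 and f0, so that clinical readers can judge which parts are plausible.
3. Obtain the standard error by delta-adjusted multiple imputation, or use SE² + δ1²·f1(1−f1)/n1 + δ0²·f0(1−f0)/n0, with n1 and n0 the numbers randomised.
4. If the existing sentence is kept, say *most conservative of the three scenarios*.
5. List the change in SAP 4.8, which now states that there are none, because the three scenarios are also protocol text. If it is made after unblinding, label the grid as post hoc.

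The cost is a little extra analysis, a declared change and a reported boundary that will look less favourable. No new data are needed.
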